## STATISTICAL ANALYSIS PLAN

---

### 2.1.3 Secondary objectives and endpoints

- To assess if procalcitonin guided de-escalation reduces antibiotic **consumption** and days of therapy with antibiotics.

- Consumption of antibiotics expressed as the Defined Daily Dosage (DDD)

*Definition of DDD: The basic definition for a defined daily dose is the assumed average maintenance dose per day for a drug used in its main indication in adults. Antibiotic use using the WHO DDD definition ([https://www.whocc.no/atc\\_ddd\\_index/](https://www.whocc.no/atc_ddd_index/)) will be determined for the most frequently prescribed Drugs in Bangladesh*

- Days of therapy with antibiotics (DOT)

Definition of DOT: One DOT represents the administration of a single antibiotic on a given day regardless of the number of doses administered or dosage strength. If a patient receives more than one antibiotic it will be added on with DOT of the first antibiotic. (Dalton et al. 2015)

- Number of days of parenteral antibiotic during hospitalisation period
- Number of days of antibiotic treatment during the hospitalisation period.

- To assess the safety of procalcitonin guided de-escalation of treatment
  - Overall mortality, mortality-associated with recurrent infection, and non-lethal recurrent infections.
- To assess the effect of procalcitonin guided de-escalation on length of hospital stay
  - Duration of hospital stay (ICU/ general ward)
- To determine the spectrum of antimicrobial resistance among bacteria identified in clinical specimens from Bangladeshi patients hospitalized with sepsis
  - Bacterial isolates from blood cultures will be identified, tested for antibiotic susceptibility. In a subset of antibiotic resistant isolates, genetic correlates of resistance will be assessed (A comprehensive microbiological analysis plan is provided in section 3.6).
- To compare the patient care costs between study arms
  - Direct medical costs of prescribed antibiotics, the PCT assay and hospital stay costs.

### 2.2 Study design

#### Brief Description

##### Trial design

Randomised controlled, non-blinded, two-arm, parallel, clinical trial comparing Standard practice to procalcitonin guided de-escalation of antibiotic therapy.

---

## STATISTICAL ANALYSIS PLAN

---

### Trial settings

Trial site is Chattogram Medical College Hospital (CMCH), Bangladesh. CMCH is a tertiary care hospital with undergraduate and postgraduate teaching facilities. This tertiary hospital receives referrals from urban and rural areas of southern Bangladesh and has basic facilities for intensive care and haemodialysis.

### Randomisation and blinding

Consecutive patients with suspected sepsis admitted at CMCH are eligible for enrolment, provided informed consent is obtained. After eligibility is confirmed, the patient is randomised to either the experimental (procalcitonin) arm or control (standard therapy) arm. Randomisation and treatment allocation is determined by a central computerized binary sequence number generator in a 1:1 ratio with pre-determined block sizes by the study statistician. The study statistician designs the randomisation schedule. The subject's randomisation number is on the sealed opaque envelope as well as on and insert inside the envelope. The trial staff opens the envelopes sequentially for enrolled trial participants and allocates the patient to the treatment arm that is denoted on the insert of that envelope. The allocated arm is noted on the eCRF and other applicable documents. The medical staff and patients are not blinded to intervention randomisation.

### 2.3 Determination of sample size

The sample size calculation is based on the expected difference in mean length of antibiotic treatment between the experimental and control arm. Based on retrospectively collected data from CMCH, the mean length of therapy (LOT) in sepsis patients was 5.2 days with a standard deviation (SD) of 8 days. The SD of the duration of antibiotic prescription in population level was derived by dividing the difference between the maximum and minimum value of LOT that was obtained from the retrospective data by four as one of the rules of thumb. The SD is assumed to be the same in the experimental and the control arms. We hypothesize to have a higher mean number of days of LOT in the control group as compared to the experimental group – i.e 5.2 days in the control group vs. 3.2 days in the experimental group, for an absolute reduction of mean LOT of 2 days. The level of significance was set at 5% (i.e., alpha=0.05). Based on these assumptions and estimating with 80% power, a total of 506 participants are required (i.e., 253 in the experimental arm and 253 in the control arm) to verify the study hypothesis. We anticipate a 5% loss to follow-up and to compensate for this, a total of 532 participants will be enrolled (266 in the experimental arm and 266 in the control arm). The sample size calculations have been performed in R software (version 4.2.1).

## STATISTICAL ANALYSIS PLAN

### 3. Data Analysis

#### 3.1 Trial Profile

The number of patients screened, reasons for non-enrolment, number of patients randomised, number of patients lost to follow-up and the number of patients assessed for final endpoint are summarised in a CONSORT flow diagram, as shown in Figure 1.

[figure not shown]

Figure 1: Consort Trial Profile by Arms

## STATISTICAL ANALYSIS PLAN

### 3.2 Demographics and other baseline characteristics

The following baseline characteristics are described, according to study arm as shown in Table 1. Continuous variables will be summarised using mean and standard deviation or median (IQR) as appropriate. Categorical variables such as sex, marital status, education, employment status, residences and infection status at baseline will be summarised using frequencies and percentages.

**Table 1. Baseline characteristics for the participants by study group**

Characteristics	Procalcitonin (N=XX)	Control (N=XX)	Total (N=XX)
Age (years), median (IQR)	XX (XX - XX)	XX (XX - XX)	XX (XX - XX)
Female, n (%)	XX (XX)	XX (XX)	XX (XX)
Weight (Kg), median (IQR)	XX (XX - XX)	XX (XX - XX)	XX (XX - XX)
Height (cm), median (IQR)	XX (XX - XX)	XX (XX - XX)	XX (XX - XX)
BMI (kg/m  ), median (IQR)	XX (XX - XX)	XX (XX - XX)	XX (XX - XX)
Marital Status, n (%)			
Married	XX (XX)	XX (XX)	XX (XX)
Single	XX (XX)	XX (XX)	XX (XX)
Widowed	XX (XX)	XX (XX)	XX (XX)
Divorced	XX (XX)	XX (XX)	XX (XX)
Highest education, n (%)			
No formal education	XX (XX)	XX (XX)	XX (XX)
Primary education	XX (XX)	XX (XX)	XX (XX)
High School	XX (XX)	XX (XX)	XX (XX)
College education	XX (XX)	XX (XX)	XX (XX)
Graduate or post-graduate	XX (XX)	XX (XX)	XX (XX)
Employment status, n (%)			
Government service	XX (XX)	XX (XX)	XX (XX)
Private sector	XX (XX)	XX (XX)	XX (XX)
Casual worker (pay by the day)	XX (XX)	XX (XX)	XX (XX)
Unemployed	XX (XX)	XX (XX)	XX (XX)
Residences, n (%)			
Urban	XX (XX)	XX (XX)	XX (XX)
Rural	XX (XX)	XX (XX)	XX (XX)
Temperature (°C), median (IQR)	XX.X (XX.X - XX.X)	XX.X (XX.X - XX.X)	XX.X (XX.X - XX.X)
Respiratory rate (breaths/min), median (IQR)	XX (XX - XX)	XX (XX - XX)	XX (XX - XX)
Heart rate (beats/min), median (IQR)	XX (XX - XX)	XX (XX - XX)	XX (XX - XX)
Systolic blood pressure (mmHg), median (IQR)	XX (XX - XX)	XX (XX - XX)	XX (XX - XX)
Diastolic blood pressure (mmHg), median (IQR)	XX (XX - XX)	XX (XX - XX)	XX (XX - XX)
SPO2	XX (XX - XX)	XX (XX - XX)	XX (XX - XX)
WBC (Total/Cmm), median (IQR)	XX (XX - XX)	XX (XX - XX)	XX (XX - XX)

**STATISTICAL ANALYSIS PLAN**

Neutrophil (%), median (IQR)	XX (XX - XX)	XX (XX - XX)	XX (XX - XX)
Infection status at enrolment, n (%)			
Suspected bacterial infection	XX (XX)	XX (XX)	XX (XX)
XXX	XX (XX)	XX (XX)	XX (XX)

**3.3 Analysis of primary outcome (length of antibiotic therapy), number of mortalities, pattern of major organ dysfunction, and recurrent infections**
**Summary of intention to treat (ITT) and per protocol analysis (PP) Inclusion and Exclusion Criteria**
**A. Included in ITT but Excluded in PP**

- a. Participants who meet exclusion criteria/alternative non-infection diagnosis during the study:
  - Outcome will be censored after the duration of empiric antibiotic therapy until the date patient receives a definitive diagnosis.
- b. Patients transferred to other hospitals:
  - Last observed outcome before transfer to the other hospital will be used
- c. Patients who left against medical advice:
  - Last observed outcome before leaving against medical advice will be used
- d. Patients without complete primary outcome data:
  - Patients that do not have complete outcome data are included in the table with baseline data.
- e. Patients who die early (before the intervention started):
- f. Patients without 28-day follow-up data:
  - Outcome data will be censored at the last day of follow-up
- g. Patients who received prophylactic antibiotics:
  - Outcome data will be censored at the day of start of prophylactic antibiotics

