### 1. Analysis Considerations

#### 1.1 General Analysis Approach

The main analysis strategy for the primary outcome will be the intention-to-treat (ITT) principle. In this analysis, patients will be analysed according to the arm of randomisation, irrespective of the treatment that was actually given. These ITT analyses will be followed by the per protocol (PP) analysis. In this analysis, only those that adhered to the protocol with respect to the primary outcome will be included for analysis of the primary outcome. All participants will be included in the Intention to Treat (ITT) analysis to maintain the balance achieved through randomisation. For the Per Protocol Analysis (PPA), patients who meet exclusion criteria before hospital discharge or who receive an alternative non-infectious diagnosis during the trial will be excluded.

Key secondary endpoints such as Days of Therapy (DOT), safety and tolerability data will be analysed similar to the ITT approach for the main primary outcome. In this analysis, patients will be analysed according to the arm of randomisation irrespective of the treatment that was actually given, and all patients will be included in the analyses irrespective of their follow-up status, provided data collection is complete. Withdrawals and losses to follow up will not affect the analyses of this data as long as the relevant data needed for these analyses is available prior to withdrawal or loss to follow up.

Data analysis will be performed using Stata 18 or higher, StataCorp, [name] or in R software.

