**STATISTICAL ANALYSIS PLAN****4.2 Atypical Cases in PROCALBAN:**

1. **Antibiotic Management:** For cases where an alternative diagnosis is confirmed, the stopping date for empirical antibiotic therapy will be recorded as the actual stop date.
2. **Alternative Diagnosis:** If antibiotic therapy is continued despite the confirmation of an alternative diagnosis, such as Melioidosis (which requires a prolonged course of antibiotics), the date on which the treating team identified this alternative diagnosis will be considered as the stopping date for the initial antibiotic treatment.
3. **Additional Diagnoses:** For cases where an additional diagnosis accompanies the initially suspected infection and antibiotic therapy is continued, the full duration of the antibiotic course will be included in the outcome analysis (e.g., Enteric Fever combined with Viral Infection).
4. **Sepsis Mimickers:** In cases where sepsis-like symptoms are attributed to other conditions, such as cancer, connective tissue diseases, or suspected/confirmed tuberculosis, the duration of empiric antibiotic treatment given before an alternative diagnosis is confirmed through clinical assessment, laboratory findings, or radiological evidence will be used for outcome analysis.
5. **Discrepancies in Diagnosis:** If there is a disagreement among investigators regarding the final diagnosis, a third investigator, who has not previously reviewed the case, will assess it to determine the most appropriate antibiotic duration based on the case's clinical details.

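### For patients given another diagnosis after randomisation, ITT length of therapy stops at the diagnosis date, so recorded and actual antibiotic days can differ by arm, in either direction

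*SAP*

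**What the plan says.** Section 1.1 makes ITT the main strategy for the primary outcome: "patients will be analysed according to the arm of randomisation, irrespective of the treatment that was actually given". Section 2.1.2 defines that outcome as days of antibiotic treatment up to 28 days after discharge. It names one reason for censoring, recurrent infection.

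Other sections set the end of LOT for patients whose diagnosis changes:

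- **Section 3.3, A.a** covers "Participants who meet exclusion criteria/alternative non-infection diagnosis during the study". They stay in ITT and leave PP, and for ITT "Outcome will be censored after the duration of empiric antibiotic therapy until the date patient receives a definitive diagnosis".
- **Appendix 4.1** lets an investigator panel decide, case by case, the longest duration that counts when another diagnosis calls for a longer or changed regimen.
- **Appendix 4.2, timepoint table**, leaves the stop date of atypical cases to discussion within the team.
- **Appendix, Atypical Cases, item 1**: "For cases where an alternative diagnosis is confirmed, the stopping date for empirical antibiotic therapy will be recorded as the actual stop date".
- **Item 2**, where antibiotics continue despite the new diagnosis: "the date on which the treating team identified this alternative diagnosis will be considered as the stopping date for the initial antibiotic treatment".
- **Item 4**, sepsis mimickers: what counts is "the duration of empiric antibiotic treatment given before an alternative diagnosis is confirmed through clinical assessment", with laboratory or radiological evidence as alternatives.

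On blinding, section 2.2 states: "The medical staff and patients are not blinded to intervention randomisation".

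**The concern.** Entry is on suspected sepsis, so some randomised patients will turn out to have something else. The SAP expects this: it has a diagnostic subgroup for viral infection, cancer, tuberculosis and connective tissue disease, and it uses melioidosis as an example of an atypical case.

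For such patients the primary outcome no longer counts antibiotic days when treatment outlasts the diagnosis. It counts days to a diagnostic label. That label is applied after randomisation, in an open-label trial whose intervention is a daily laboratory result, and clinical assessment alone can confirm it. Nothing in the SAP makes the date independent of arm, and neither the panel nor the team that fixes countable duration is said to be blinded.

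The arms can then differ in recorded LOT with equal antibiotic use, or differ less than they truly do. Neither planned analysis would show it, because A.a patients are truncated in ITT and absent from PP.

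**Working it through.** **The plan's own figure.** Inputs from section 2.3: difference 2 days (5.2 v 3.2), SD 8, alpha 0.05 (two-sided assumed; the SAP does not say), power 80%. Per arm, n = 2 × (1.96 + 0.842)² × 8² / 2² ≈ 251.2, so 252. The t-test version gives 252.13, rounded up to 253 per arm and 506 in total, as stated. The sample size is not in dispute. At 253 per arm, SE = 8 × √(2/253) = 0.711 day.

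**What truncation does.** Let R_C and R_P be the mean antibiotic days removed per randomised patient in the control and procalcitonin arms. Then

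recorded difference (control − procalcitonin) = true difference − (R_C − R_P).

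The cut is harmless only if R_C = R_P. Two hypothetical pairs of patients show both directions:

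| | Procalcitonin patient | Control patient | True difference | Recorded difference |
|---|---|---|---|---|
| Exaggeration | treated 10 d, diagnosed day 3, LOT 3 | treated 10 d, diagnosed day 8, LOT 8 | 0 | 0 − (2 − 7) = 5 |
| Shrinkage | stopped day 3, LOT 3 | treated 10 d, diagnosed day 5, LOT 5 | 7 | 7 − (5 − 0) = 2 |

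**Size of a false difference.** With equal use, and a share p of each arm whose diagnosis dates differ by d days, the false difference is p × d. Neither p nor d is in the SAP; both are assumed. The false-positive rate is P(|Z + p·d/0.711| > 1.96), treating the test as a normal comparison of means.

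| p | d (days) | p × d (days) | Share of 2 days | False-positive rate |
|---|---|---|---|---|
| 5% | 2 | 0.10 | 5% | 5.2% |
| 10% | 3 | 0.30 | 15% | 7.1% |
| 15% | 5 | 0.75 | 37.5% | about 18% |

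**Size in the other direction.** Suppose the same amounts are removed in excess from the control arm. A true 2-day effect is recorded as 2 − 0.10 = 1.90 down to 2 − 0.75 = 1.25 days. With the SD unchanged, power is Φ(1.90/0.711 − 1.96) ≈ 76% down to Φ(1.25/0.711 − 1.96) ≈ 42%, against 80% planned.

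**The rules side by side.** For a patient with a sepsis mimicker whose antibiotics continue, section 3.3 A.a and item 4 end LOT at the diagnosis. The timepoint table leaves it to the team. If the new diagnosis also alters the regimen, Appendix 4.1 sends the case to a panel. Item 1, read alone, uses the actual stop of empirical therapy. Section 2.1.2, read alone, counts every day to the end of follow-up. These can give different values for the same patient.

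**The case against.** The strongest defence is that the truncated outcome is a deliberate choice. Days given for another disease are not what a de-escalation rule for the presenting infection acts on, and a few long courses could swamp the comparison. The cost of counting them is real. If 2 to 5% of patients add 30 days, and the SD of 8 does not already include such patients, the SD rises to √(64 + 0.02 × 0.98 × 900) = 9.0 up to √(64 + 0.05 × 0.95 × 900) = 10.3. Power at 253 per arm then falls from 80% to about 70% and 59%. That stands, and it is why the untruncated analysis is asked for beside the truncated one rather than in its place.

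It can also be said that the rule is stated openly and that every patient is analysed in the randomised arm. That is right; nothing is concealed. The cut also has limited reach: where antibiotics stop at the diagnosis, recorded and actual LOT agree, and item 3 of the atypical cases counts the full course when a further diagnosis accompanies the suspected infection.

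A reader might infer that procalcitonin results bring the diagnosis forward and so favour the intervention. The SAP does not support that. It never says procalcitonin moves the date, and does not say whether control-arm staff see the values. A low value that prompts a new label may also prompt stopping, in which case no days are cut. Continued treatment past the diagnosis could be commoner in the control arm, which biases toward no effect.

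None of this answers the disagreement between the stop-date rules, or the absence of any analysis that shows how much truncation matters.

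**Conclusion.** The point stands in a limited form. Ending ITT LOT at a diagnosis date set after randomisation by unblinded staff can make recorded LOT differ from antibiotic days given, by arm and in either direction. The rule goes beyond the single censoring reason in section 2.1.2, and the SAP holds several incompatible stop-date rules for these patients.

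The size is unknown. Under the assumed 5 to 15% and 2 to 5 days it is 0.10 to 0.75 day of a 2-day effect, negligible at the low end and material at the high end. The documents establish neither that the bias favours the intervention nor that truncation is indefensible as a primary rule. What they do establish is that the reader of the results could not tell.

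**What to change.** - Reconcile section 2.1.2, section 3.3 A.a, Appendix 4.1, the timepoint table and the atypical-case items into one stop-date rule for deriving LOT, and list every censoring reason in the endpoint definition.
- State that any panel or team decision on countable duration is made without knowledge of arm and procalcitonin values.
- Pre-specify an ITT analysis of LOT to the actual antibiotic stop date for these patients, bounded by 28 days after discharge and where the date is recorded. Report it beside the truncated analysis.
- Report by arm the number truncated, the time from enrolment to diagnosis, and the antibiotic days removed.

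Moving the truncation to the PP analysis would not work, because sections 1.1 and 3.3 exclude the A.a patients from PP.

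Cost: SAP wording, one further derivation from antibiotic dates, and a small table. Dates after transfer or leaving against medical advice will be missing, as Appendix 4.1 acknowledges. The untruncated analysis will have a wider spread from a few long courses and hence less power. The sample size need not change.

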**B. Included in Both ITT and PP**

- a. Patients for whom the non-binding advice to stop antibiotics was not followed:
  - Provided the patient does not meet criteria for an alternative diagnosis
- b. Patients presenting with recurrent infections:
  - If it is a recurrent infection the outcome will be censored at the time of recurrent infection. The amount of antibiotic a patient receives after enrollment in the study, up until the occurrence of a recurrent infection episode, will be included in the analysis
- c. Patients discharged before procalcitonin reached the predefined target value for antibiotic de-escalation
- d. Patients who restarted antibiotics without having a recurrent infection:

## STATISTICAL ANALYSIS PLAN

- Included in the analysis, except if antibiotics were started after discharge from CMCH for other reasons than a recurrent infection.

### C. *Pre-defined Subgroups:*

#### 1. **By source of infection:**

There will be two subgroup analyses:

- The first will be based on the initial diagnosis made by the study team.
- The second will be based on the updated final diagnosis, with the same categorisation structure as used in the initial diagnosis for the source of infection.

#### **Categories of diagnostic subgroups:**

##### **Urinary Tract Infection (UTI):**

This category will encompass all infections involving the urinary tract, including pyelonephritis, and other related infections.

##### **Skin and Soft Tissue Infection:**

Any infection primarily affecting the skin, subcutaneous tissues, or muscles will be classified under this category. This includes cellulitis, abscesses, and other similar conditions.

##### **Undifferentiated Sepsis:**

In cases where sepsis is present without a clearly identifiable source, the diagnosis will be labeled as "Undifferentiated Sepsis."

##### **Enteric Fever:**

Both suspected and microbiologically confirmed cases of enteric fever will be grouped under this diagnosis. This ensures uniformity whether or not laboratory confirmation has been obtained.

##### **Lower Respiratory Tract Infection (LRTI):**

All infections involving the lower respiratory tract, including pneumonia, exacerbations of chronic obstructive pulmonary disease (COPD), bronchiectasis, and interstitial lung disease, will be categorized as LRTI.

##### **Upper Respiratory Tract Infection (URTI):**

Infections of the upper respiratory tract, such as acute tonsillitis, and similar conditions, will fall under this label.

##### **Meningoencephalitis:**

This diagnosis will be used for infections involving the central nervous system, specifically those affecting the meninges and/or the brain, such as meningitis and encephalitis.

##### **Intra-abdominal Infection:**

This category includes infections within the abdominal cavity, such as acute gastroenteritis, cholangitis, and other intra-abdominal infectious processes.

##### **Other diagnostic subgroups (viral infections, cancer, tuberculosis, connective tissue disease)**

---

**STATISTICAL ANALYSIS PLAN**

---

**2. By presence of bacterial culture positivity:**

- Culture-positive sepsis
- Culture-negative sepsis
- **Note:** in this subgroup analysis we will exclude infections that require standardised prolonged therapy (e.g., *Burkholderia*).

